- An AST or ALT value that is greater than or equal to 3 X the ULN and an elevated total bilirubin value that is greater than or equal to 2 X the ULN and, at the same time, an alkaline phosphatase value that is less than 2 X the ULN, as determined by way of protocol-specified laboratory testing or unscheduled laboratory testing. **NOTE:** Patients will be discontinued from study therapy but followed for safety until the abnormal value(s) has/have normalized, stabilized, or returned to baseline;
- If the QTc interval change from Baseline is greater than 60 msec or the QTc interval is ≥ 500 msec (refer to Section 7.1.2.5 for details on ECG testing).

A subject who develops a superficial fungal infection (e.g., cutaneous fungal infection, thrush or candidal vaginitis) may be treated with topical antifungal agents (nystatin and/or azole formulations) and continued on study drug if in the judgment of the investigator there is no evidence of systemic involvement or more extensive mucosal involvement that would require more specific systemic antifungal therapy. Superficial candidiasis (including signs and symptoms and supportive laboratory findings) must be noted on the eCRF. It is the right and duty of the investigator or subinvestigator to interrupt treatment of any subject if he/she feels that study discontinuation is necessary to protect the subject, or that there are unmanageable factors, that may interfere significantly with the study procedures or interpretation of the results.

If a subject discontinues prior to completion of the study, the reason for the discontinuation will be obtained. The date of the last dose of study medication and the date of the last assessment and/or contact will be obtained. This information will be documented in the appropriate section of the eCRF. A follow-up contact (telephone or visit) will be arranged as appropriate.

At the time of discontinuation, every effort should be made to ensure all procedures and evaluations scheduled for the final study visit are performed (see Section 6.0, Trial Flow Chart). For all discontinued subjects, a trough sample should be collected within 24 hours of the last dose, AEs should be recorded and followed to outcome and medication compliance should be assessed.

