7.1.2.5 Electrocardiogram

Two baseline ECGs must be performed at least 5 minutes apart at the Baseline Visit for purposes of protocol eligibility.

Prior to study drug administration, all ECGs should be reviewed for clinically significant abnormalities and reported as normal (or with findings that are not clinically significant).

ECGs should also be performed on Day 6, 7 or 8 of POS IV solution treatment and on Day 8, 9, or 10 of POS PFS treatment and as clinically indicated for the evaluation of AEs.

ECGs performed after the Baseline Visit should be done at approximately the same time of day (AM or PM) that baseline ECGs were performed.

A standard 12-lead ECG, reporting ventricular rate, PR, QRS, QT, and QTc intervals, will be performed. Any clinically significant abnormality must be followed until stabilization or return to baseline.

Any change in the QTc interval of greater than 30 msec post Baseline (when compared to Baseline) will require a repeat ECG, and a determination of serum potassium (K), calcium (Ca), magnesium (Mg), and electrolyte replacement, if necessary. Additional evaluation may be required, and the principal investigator should determine if discontinuation of study drug or other evaluation is required in consultation with the project physician.

If the QTc interval change from Baseline is greater than 60 msec, study drug should be interrupted while evaluation and treatment of other etiologies is ongoing (Section 5.8, Subject Discontinuation Criteria).

During the Treatment Phase, if a QTc interval is found to be abnormal (symptomatic QTc intervals greater than 450 msec [males] or 470 msec [females]) after repeated ECG for

confirmation a cardiology consultation is to be requested to determine possible etiologies in addition to or other than study drug should also be performed at the same time (e.g., review of other concomitant drugs, and determination of serum Mg, Ca, and K levels). The investigator will determine if discontinuation of study drug is warranted after clinical examination of the subject and pertinent laboratory evaluation, and discussion of the case with the Sponsor's project physician.

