ECGs performed will be transferred to a blinded third party for an evaluation of QT, QTc (Fredericia and Bazett), PR, and QRS intervals and ventricular rate, as well as an overall clinical interpretation. The final results of the third-party analysis will be considered the definitive ECG data and will be the only ECG data used in the analysis.

Note: When the collection of vital signs, ECGs, and PK samples coincide, the blood samples for PK determination should be collected first (so that the PK samples are collected on time), followed by the vital signs, and then the ECG. It is preferred that the ECG be performed at the same time each day (e.g., morning) to reduce diurnal variation.

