8.2.2 Safety Analyses

All subjects who receive at least one dose of study drug will be included in the safety analysis.

Adverse events (AEs) will be tabulated by age (2 to <7 years, 7 to 17 years) and POS treatment (IV solution, PFS). The number and percent of each event will be computed and summarized by body system organ class. Severity, duration, relationship to POS, and outcome of the events will also be recorded. ECGs and clinical safety laboratory values, such as hematology and serum chemistry, will be tabulated by age and treatment group and compared to baseline using summary statistics. Vital signs will be listed by date and time. Key toxicities, including hepatotoxicity and nephrotoxicity, will be tabulated by age and dose cohorts.

Additionally, survival at Day 100 (allowed range Day 90 -110) and Day 65 (allowed range Day 60-70) will be tabulated by age group and dose cohort.

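### Section 8.2.2 plans no count of children who cross the protocol's own QTc limits, and its ECG table may pool the three dose cohorts

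*Combined protocol and SAP*

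**What the plan says.** During the trial, QTc is managed by limits applied to each child.

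- Section 7.1.2.5: "Any change in the QTc interval of greater than 30 msec post Baseline (when compared to Baseline) will require a repeat ECG", together with electrolyte checks.
- Section 7.1.2.5: "If the QTc interval change from Baseline is greater than 60 msec, study drug should be interrupted" while other causes are worked up.
- Section 5.8, in the list of reasons for which treatment must be discontinued: "If the QTc interval change from Baseline is greater than 60 msec or the QTc interval is ≥ 500 msec".

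The ECG data are also set out in Section 7.1.2.5. At baseline, "Two baseline ECGs must be performed at least 5 minutes apart at the Baseline Visit". On treatment, "ECGs should also be performed on Day 6, 7 or 8 of POS IV solution treatment", once more on Day 8, 9 or 10 of PFS, and whenever clinically indicated. A blinded third party reads the ECGs with both the Fridericia and the Bazett correction, and its readings "will be the only ECG data used in the analysis".

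The analysis in Section 8.2.2 is one clause, shared with the safety laboratory values: they "will be tabulated by age and treatment group and compared to baseline using summary statistics". The same section counts adverse events by age and by formulation (IV solution, PFS). It tabulates key toxicities by age and dose cohort, naming hepatotoxicity and nephrotoxicity as included. Section 3.2 states that safety parameters will be summarised by age group and dose cohort. Section 8.1 rules out a stand-alone SAP.

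**The concern.** QTc risk shows itself as a large change in one child, and the protocol treats it that way. The analysis does not carry the limits over. A reader of the report could then be unable to learn from the planned tables how many children met a limit that called for a repeat ECG, an interruption or a discontinuation.

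The dose breakdown is also uncertain. If treatment group in the ECG clause means formulation, the 3.5, 4.5 and 6 mg/kg cohorts are combined within each age group. A signal confined to one dose would be diluted, and the secondary objective in Section 3.2 would not be met for ECGs. This matters most for Dose Cohort #3: it is the highest dose, it was set at a minimum of 36 subjects to strengthen the safety database (Summary of Changes), and it has no formal interim analysis (Section 8.2.6).

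**Working it through.** **The plan's own figure.** The documents give no QTc mean, standard deviation or event rate, so there is no figure on this point to reproduce. The only probability in the plan (Section 8.2.5, at least 10 of 12 with p = 0.90) recomputes to 0.889, matching the stated 89%. It concerns Cavg and is not used below.

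**Limits against planned outputs.**

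| Limit in the protocol | Where | Counted in Section 8.2? |
|---|---|---|
| Change >30 msec | 7.1.2.5 | No |
| Change >60 msec | 5.8 and 7.1.2.5 | No |
| Value ≥500 msec | 5.8 | No |

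**Other routes to a count.**

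- Adverse-event table (8.2.2): shows a QTc case only if the investigator reports it as an adverse event, and is split by age and formulation, not dose.
- Key toxicities (8.2.2): the list is open-ended but does not name QTc.
- Events of clinical interest (7.2.3.2): overdose and a liver-test rule only.
- Azole-associated toxicity (4.2.4.2): to be evaluated, with no QTc rule.
- Reason for discontinuation (5.8): recorded on the eCRF, but Section 8.2 plans no table of reasons.

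**Does the ECG table pool doses?** In the adverse-event sentence of 8.2.2, treatment is spelled out as IV solution or PFS. Section 1.0 instead uses treatment groups for the two age groups, with dose cohorts within them. The ECG clause already names age separately, so formulation is the more natural reading, but the text does not settle it.

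**Illustration of masking.** Inputs from the documents: n = 12, the minimum of PK-evaluable subjects per age group and dose cohort (8.2.5), and n = 36, the minimum per age group over three cohorts (2.1; the 12 extra subjects in Dose Cohort #3 can raise it). Assumptions: one child at +65 msec, and the others averaging m = 0, 5 or 10 msec.

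Mean = (65 + (n − 1)m)/n. The one child moves the mean by (65 − m)/n.

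| m (msec) | Mean, n = 12 | Shift, n = 12 | Mean, n = 36 | Shift, n = 36 |
|---|---|---|---|---|
| 0 | 65/12 = 5.4 | 5.4 | 65/36 = 1.8 | 1.8 |
| 5 | 120/12 = 10.0 | 60/12 = 5.0 | 240/36 = 6.7 | 60/36 = 1.7 |
| 10 | 175/12 = 14.6 | 55/12 = 4.6 | 415/36 = 11.5 | 55/36 = 1.5 |

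A count shows the same child as 1/12 = 8.3% (exact 95% CI 0.2 to 38.5%) or 1/36 = 2.8% (0.1 to 14.5%). A count of zero is also informative: the upper 97.5% limit, 1 − 0.025^(1/n), is 26.5% at n = 12 and 9.7% at n = 36.

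**What a count would still need.** Section 5.8 does not say which correction its limits use, and the third party supplies two. No rule combines the two baseline ECGs. Since only third-party readings are analysed, a child acted on from a site reading may not exceed the limit in the analysis data.

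**The case against.** The strongest reply is that this is an open-label Phase 1B estimation trial. Each child is protected in real time by Sections 5.8 and 7.1.2.5, and an external committee reviews safety. The third-party readings permit a count at any time. That stands: the gap is in planned reporting, not in subject protection.

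A reader might also infer four stronger things that the documents do not support.

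- **That a child stopped for QTc disappears from the record.** All adverse events from allocation to 14 days after treatment must be reported (7.2), Table 9 records whether an event led to discontinuation, and 5.8 requires the reason for early discontinuation. The case may surface by these routes. None guarantees a count in a planned table.
- **That only means will be reported.** Section 8.2.2 does not say so. In the n = 12 illustration with all others exactly 0, the maximum is +65 msec and the SD is √[(65² − 12 × (65/12)²)/11] = 18.8 msec. A reported maximum would reveal the child. The fair criticism is that the statistics are unspecified.
- **That repeat and unscheduled ECGs are left out.** Section 8.2.2 does not specify a by-visit summary, and 7.1.2.5 sends ECGs to the third party without restricting them to scheduled ones. Their use is unstated, not excluded.
- **That the PFS summary is biased towards no effect because children stopped on IV have no PFS ECG.** This presumes permanent stopping. For a change above 60 msec, 5.8 lists discontinuation and 7.1.2.5 describes interruption. A stopped child's IV reading also stays in the IV summary, and the PFS summary describes those who took PFS.

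**Conclusion.** The point holds as a gap in the planned analysis. The protocol sets three QTc limits for individual children. Section 8.2.2 counts against none of them, leaves its summary statistics unnamed, and does not clearly deliver the dose-cohort breakdown promised in Section 3.2. No other planned output guarantees the count.

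The size can only be illustrated. One child at +65 msec with the others at 0 shifts a mean by 5.4 msec among 12 children and 1.8 msec among 36. The +65 msec and the average of the other children are assumptions. The n = 12 cell is the age-by-dose cell, which the ECG clause may not use; n = 36 applies if doses are pooled. The documents do not show that any case has been or will be lost. Adding the count is a cheap improvement that the sponsor should make.

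**What to change.** Keep the summary statistics, name them, and add to Section 8.2.2 text to this effect:

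> The number and percent of subjects whose worst post-baseline third-party-read QTc (scheduled, repeat and unscheduled ECGs) shows a change >30 msec, a change >60 msec or a value ≥500 msec will be tabulated by age group, dose cohort and formulation at the time of the ECG. Counts will be given for both the Fridericia and the Bazett correction. Baseline is the mean of the two Baseline-visit ECGs. Every subject whose study drug was interrupted or discontinued for QTc will be listed, including those acted on from a site reading.

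If a row for values >450 msec (males) or >470 msec (females) is wanted, label it as a count of values. The protocol's own criterion at those levels applies to symptomatic prolongation, so the two should not be confused.

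Separately, Sections 5.8 (discontinue) and 7.1.2.5 (interrupt) differ for a change above 60 msec and must be reconciled. The listing should show which action was taken.

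The cost is a short protocol change, one extra table and one listing, from ECGs already collected and centrally read. No new procedure is needed.

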8.2.3 Efficacy Analyses

There are no efficacy analyses planned for this study.

8.2.4 Other Analyses

Compliance with study medication, including palatability/acceptability of the POS PFS formulation, will be summarized by age and treatment group.

8.2.5 Power and Sample Size

The sample size is not based on any formal power calculation.

The total sample size for the study is a minimum of 84 subjects (72 PK-evaluable subjects) distributed across the 3 dose cohorts as follows:

Dose cohort #1 (a minimum of 24 PK evaluable subjects, divided 12 per Age Group).

Dose cohort #2 (a minimum of 24 PK evaluable subjects, divided 12 per Age Group).

Dose cohort #3 (a minimum of 36 subjects, divided as 12 PK evaluable subjects per Age Group and an additional 12 distributed across either Age Group).

The actual total number of enrolled subjects may be greater than 84 in order to ensure a minimum of 72 subjects that meet PK evaluability criteria.

At the time of this amendment (MK-5592-097-02), enrollment in Dose Cohorts #1 and #2 is complete. Therefore, the remaining target enrollment for this amendment is a minimum 36 subjects in Dose Cohort #3 (12 PK evaluable subjects per age group and an additional 12 distributed across either age group).

If successful dose selection is defined as at least 10 out of 12 (82.2%) patients per age/dose group achieving a $C_{avg} > 500$ ng/mL, the chance of achieving success is at least 89%, based on a sample size of 12 patients in each age/dose cohort using a binomial distribution ($n=12$, $p=0.90$), where p = probability of success.

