4.2.2 Rationale for Dose Selection/Regimen

Rationale for dose cohorts 1 and 2 included in original protocol version, MK-5592-097-00

The starting dose of 3.5 mg/kg/day for the POS IV solution and POS PFS formulation was projected via modeling and simulation to achieve the pharmacokinetic (PK) target of an average concentration (C_{avg}) of between 500 and 2500 ng/mL in approximately 90% of patients 2 to 17 years of age (see Section 4.2.3 for details regarding the PK target). In this

study, if at least 10 out of 12 PK-evaluable patients in a dose cohort achieve a C_{avg} in the specified range the PK exposure target will be considered to have been met.

Specifically, utilizing population PK models developed for the POS IV solution and the POS PFS formulation based on observed adult PK data, simulations were conducted to project the exposure in the pediatric population. The PK profile of the POS PFS formulation is expected to be comparable to the POS tablet, based on results of a biocomparison study conducted in adults. The PK concentration versus time profile in the pediatric population was projected by allometrically scaling model parameters by body weight, and simulating the resulting profiles, then calculating the distribution of projected C_{avg} values for each formulation for young children (2 to <7 years) and adolescents (7 to 17 years).

For the POS IV solution, a dose of 3.5 mg/kg/day was expected to result in 91% of young children (2 to <7 years) and 96% of adolescents/older children (7 to 17 years) with C_{avg} values within the target range of 500 and 2500 ng/mL. For the POS PFS formulation, 85% of young children (2 to <7 years) and 90% of adolescents (7 to 17 years) were expected to achieve the PK target.

For the POS IV solution, a dose of 4.5 mg/kg/day was expected to result in 94% of young children (2 to <7 years) and 88% of adolescents/older children (7 to 17 years) with C_{avg} values within the target range of 500 and 2500 ng/mL. For the POS PFS formulation, 90% of young children (2 to <7 years) and 86% of adolescents/older children (7 to 17 years) were expected to achieve the PK target.

Rationale for the addition of third dose cohort (6 mg/kg) in Amendment MK-5592-097-02

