At the time of this amendment, MK-5592-097-02, the 3.5 mg/kg and 4.5 mg/kg dose cohorts have completed enrollment. Based on interim analysis, although the 4.5 mg/kg dose cohort achieved the primary PK target of ~90% of subjects having a steady state C_{avg} POS concentration between 500 and 2500 ng/mL for both the IV solution and oral PFS formulations in both age groups (see [Table 1](#)), the overall exposures (as measured by mean C_{avg} concentrations) were markedly lower than the exposure seen in adult studies of the POS tablet (see [Table 2](#)). Specifically in Age Group 1, mean C_{avg} values were approximately 30-40% lower than what was seen in an adult study of the oral tablet (1080 ng/mL and 976 ng/mL for the IV and PFS, respectively, compared with 1580 ng/mL for the tablet). Therefore, in an effort to achieve systemic POS exposure more closely aligned with the exposure profile in adults, a third dose cohort (6 mg/kg, up to a maximum of 300 mg) is being added to the study.

The selection of the 6 mg/kg/day for Dose Cohort #3 was supported by a modeling and simulation analysis, which predicted the geometric mean C_{avg} and the fraction of subjects with C_{avg} falling within the target range of 500-2500 ng/mL at higher doses for each formulation and age group. Specifically, a population PK model was developed for the IV and PFS formulation based on observed pediatric PK data in Dose Cohorts 1 and 2 (3.5 and 4.5 mg/kg, respectively) and simulations were conducted to project the exposure in the same pediatric age groups for each formulation at doses of 6 and 7.5 mg/kg.

For the POS IV solution, a dose of 6 mg/kg/day is expected to result in 97% of subjects in Age Group 1 (2 to <7 years) and 87% of subjects in Age Group 2 (7 to 17 years) with C_{avg} values within the target range of 500 and 2500 ng/mL. Geometric mean C_{avg} values for IV are predicted to be 1343 ng/mL and 1651 ng/mL for Age Groups 1 and 2, respectively. For the POS PFS formulation, 83.5% of Age Group 1 (2 to <7 years) and 82% of Age Group 2 (7 to 17 years) are expected to achieve the PK target. Geometric mean C_{avg} values for PFS are predicted to be 847 ng/mL and 1083 ng/mL for Age Group 1 and 2, respectively.

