4.2.3 Rationale for Pharmacokinetic Targets

The minimum desired target level of the steady-state POS plasma concentration for this study is based on observations from earlier registration clinical trials conducted with the POS oral suspension in adult patients (Table 3).

Table 3 Posaconazole Exposures at Steady State During Treatment with Posaconazole Oral Suspension from Pivotal Trials Supporting Safety and Efficacy in Adult Patients

	Mean C _{avg} ng/mL	Lower Bound 2 nd Quartile ng/mL	99 th Percentile ng/mL
Prophylaxis of IFIs (600 mg/day)			
Neutropenic subjects (AML/MDS)	583	322	1920
GVHD subjects	1130	557	3260
Treatment of IFIs (800 mg/day)	808	290	2990

C_{avg} = average plasma concentration; GVHD = graft-versus-host disease; IFI= invasive fungal infections; AML = acute myelogenous leukemia; MDS = myelodysplastic syndrome

In a controlled trial involving neutropenic adult subjects (study P01899), POS oral suspension was superior to standard azoles (fluconazole and itraconazole) in reducing the incidence of IFI, including aspergillosis and candidiasis, and in reducing 100-day all-cause mortality; in this study, the mean plasma concentration at steady state was 583 ng/mL. POS oral suspension was also found to be effective for the treatment of adult subjects with refractory IFI, including aspergillosis, and for the treatment of IFI in adult subjects who were intolerant to certain antifungals (study P00041). POS oral suspension showed a better response rate and survival benefit when compared to historical control cases; in this study, the mean plasma concentration was 808 ng/mL.

There appeared to be an association between POS plasma concentration achieved with POS oral suspension at steady state and efficacy in these pivotal clinical trials. In general, adult subjects with POS steady state exposures in the second quartile or higher had higher response rates than control (Table 4). Using these data and following receipt of regulatory guidance, a mean steady state C_{avg} exposure of approximately 1200 ng/mL with approximately 90% of subjects with values between 500 and 2500 ng/mL has been proposed as a target exposure for the POS pediatric program.

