Since there is evidence that efficacy is correlated to exposure, with lower exposures being associated with poor outcomes, and the cumulative data to date does not suggest any toxicities are associated with $C_{avg} > 2500$ ng/mL, the primary goal is to ensure that most pediatric subjects achieve a steady-state C_{avg} that is > 500 ng/mL.

Table 4 Clinical Response Rates by C_{avg} Quartile Analyses from Pivotal Trials of POS Oral Suspension Supporting Safety and Efficacy in Adult Patients

Quartile	CI98-316 Prophylaxis in GVHD		P01899 Prophylaxis in Neutropenia (AML/MDS)		P00041 Treatment - Aspergillosis	
	C_{avg} Range	Clinical Failure	C_{avg} Range	Clinical Failure	C_{avg} Range	Clinical Success
Q1	21.5 – 557	44.4% 28/63	89.6 – 322	54.7% 29/53	55 – 277	24% 4/17
Q2	557 – 915	20.6 % 13/63	322 – 490	37% 20/54	290 – 544	53% 9/17
Q3	915 – 1563	17.5% 11/63	490 – 734	46.3% 25/54	550 – 861	53% 9/17
Q4	1563 – 3650	17.5% 11/63	734 – 2200	27.8% 15/54	877 – 2010	71% 11/16
Control	--	35%	--	42%	--	26%

Shaded area = Targeted exposure in 90% of subjects
 C_{avg} = average plasma concentration; GVHD = graft-versus-host disease; AML = acute myelogenous leukemia; MDS = myelodysplastic syndrome

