5.9 Subject Replacement Strategy

If a subject in a given dose cohort and age group fails to complete 7 days of IV study therapy, a replacement subject will be entered at that dose cohort and age group. Subjects will not be re-enrolled in this study.

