8.2 Statistical Analysis Plan

8.2.1 Pharmacokinetic Analysis Plan

Only subjects who receive at least 7 days of POS IV solution therapy and complete the full POS PK sampling while on POS IV solution will be included in the non-compartmental PK analysis for the primary patient population.

PK parameters for POS (C_{max} , C_{min} , C_{avg} , CL) will be listed and summarized by POS formulation, dose cohort, and age group using descriptive statistics.

For POS PFS therapy, a population PK analysis will be conducted to determine the individual PK exposure. A population PK model will be developed using the plasma data collected from this study in combination with the adult PK data. Model-predicted individual concentration-time profiles will be used to determine C_{max} , C_{min} , C_{avg} , AUC and CL/F for patients receiving POS PFS. Covariates of age group and dose cohort will be explored in the model.

Comparison of the exposure from previous experience in adults (from P05520 for the POS IV formulation; P05615 for the tablet formulation) will be conducted at steady state using graphics. Additionally, the proportion of subjects in PN097 with steady-state C_{avg} greater than or equal to 500 ng/mL (as well as the proportion of subjects with C_{avg} between 500-2500 ng/mL) will be compared to the previous studies using descriptive statistics.

A non-compartmental PK analysis will be performed to determine the PK exposure of sulfobutylether-beta-cyclodextrin-containing (SBE β CD). PK parameters for POS (C_{max} , T_{max} and AUC) will be listed and summarized by POS dose cohort, and age group using descriptive statistics.

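### Section 8.2.5 misprints 10/12 as 82.2%, applies the 10-of-12 rule to a different Cavg criterion from Section 4.2.2, and gives as a minimum an 89% that is the value only at p = 0.90

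*Combined protocol and SAP*

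**What the plan says.** Section 8.2.5 states that the sample size has no formal power basis. It then offers a definition of success, "at least 10 out of 12 (82.2%) patients per age/dose group" with Cavg above 500 ng/mL and no upper limit, and continues: "the chance of achieving success is at least 89%, based on a sample size of 12 patients in each age/dose cohort". The calculation named there is binomial with n = 12 and p = 0.90.

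Section 4.2.2 states the rule differently. The PK exposure target counts as met "if at least 10 out of 12 PK-evaluable patients in a dose cohort achieve" a Cavg in the specified range, which that section gives as 500 to 2500 ng/mL. The sentence sits under the rationale for Dose Cohorts #1 and #2 but is worded for the study as a whole.

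The supporting text uses both criteria. Section 4.2.3 gives a target for the mean Cavg (about 1200 ng/mL) and one for its spread: "approximately 90% of subjects with values between 500 and 2500 ng/mL has been proposed as a target exposure for the POS pediatric program". Section 4.2.2 describes about 90% within 500 to 2500 ng/mL as the primary PK target when it reports the interim result. Section 4.2.3 also says that "the primary goal is to ensure that most pediatric subjects achieve a steady-state" Cavg above 500 ng/mL. Section 8.2.1 will report both proportions: at or above 500 ng/mL, and the share "between 500-2500 ng/mL) will be compared to the previous studies using descriptive statistics".

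For Dose Cohort #3, Section 4.2.2 predicts 97% (Age Group 1) and 87% (Age Group 2) in range for IV. It adds: "For the POS PFS formulation, 83.5% of Age Group 1 (2 to <7 years) and 82% of Age Group 2".

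**The concern.** The printed percentage does not match its own fraction. More substantively, one numerical rule is attached to two events. If 9 of 12 subjects were in range and 3 were above 2500 ng/mL, the result would be 12 of 12 under Section 8.2.5 and 9 of 12 under Section 4.2.2: a pass and a fail from the same data. The p = 0.90 in Section 8.2.5 also matches the programme target of about 90%, which Section 4.2.3 states for the range and not for the lower limit alone.

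Calling 89% a minimum requires p of about 0.90 or more in every age/dose group. The predictions made for 6 mg/kg do not show that. At stake is how a reader judges the Cohort #3 result: which version applies, and how likely success was expected to be. Section 8.1 says that no separate SAP will be issued, so these sections are where a reader would look.

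**Working it through.** **The plan's own figures.** 10/12 = 0.8333, so 83.3%, not 82.2%. For X binomial with n = 12 and p = 0.90:

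P(X ≥ 10) = 66 × 0.90^10 × 0.10^2 + 12 × 0.90^11 × 0.10 + 0.90^12 = 0.2301 + 0.3766 + 0.2824 = 0.889.

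The stated 89% is reproduced and does not depend on the misprint. The function rises with p: 0.862 at p = 0.89, 0.889 at 0.90, 0.913 at 0.91. Exactly 0.890 needs p = 0.9003.

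**In-range version (Section 4.2.2 rule).** The same formula with the 6 mg/kg predictions from Section 4.2.2:

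| Cell | Predicted share in 500–2500 ng/mL | P(at least 10 of 12) |
|---|---|---|
| IV, Age Group 1 | 0.97 | 0.995 |
| IV, Age Group 2 | 0.87 | 0.80 |
| PFS, Age Group 1 | 0.835 | 0.68 |
| PFS, Age Group 2 | 0.82 | 0.63 |

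Three of the four cells are below 0.89. No distributional assumption is needed beyond taking the predictions as p.

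**Above-500 version (Section 8.2.5 rule).** The documents give no P(Cavg > 500) at 6 mg/kg, so what follows rests on assumptions. Write P(> 500) = in-range share + u, where u is the share above 2500 ng/mL.

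*PFS, Age Group 1, varying u:* u = 0 gives 0.68; u = 0.016 gives 0.74; u = 0.05 gives 0.85; u = 0.065 gives 0.89.

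*PFS, Age Group 1, lognormal fit.* Take the predicted geometric mean of 847 ng/mL and solve Φ(ln(2500/847)/σ) − Φ(ln(500/847)/σ) = 0.835. This gives σ = 0.506, P(> 500) = 0.851 and P(> 2500) = 0.016, and so P(at least 10 of 12) = 0.74.

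*PFS, Age Group 1, scaling the observed values in Table 2* (dose-proportional, lognormal, σ² = ln(1 + GCV²)). The scaled geometric means are 511 × 6/3.5 = 876 (n = 5, GCV 36.0%) and 976 × 6/4.5 = 1301 (n = 7, GCV 64.4%).

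| Geometric mean | GCV | P(> 500) | P(at least 10 of 12) |
|---|---|---|---|
| 876 | 36.0% (own) | 0.946 | 0.976 |
| 1301 | 64.4% (own) | 0.948 | 0.978 |
| 876 | 64.4% (crossed) | 0.829 | 0.66 |
| 1301 | 36.0% (crossed) | 0.997 | about 1.00 |

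The range for this cell is therefore about 0.66 to 1.00, on either side of 0.89.

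*Other cells, same lognormal fit:* PFS Age Group 2 has P(> 500) = 0.901 and P(at least 10 of 12) = 0.893. IV is about 1.00 in both age groups. For IV Age Group 2 the version matters: 0.80 in range against about 1.00 above 500, because the fit puts about 13% above 2500 ng/mL.

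**How often the versions differed so far.** The cells of Table 1 sum to 11 + 5 + 19 + 10 + 13 + 7 + 14 + 8 = 87 Cavg values, of which 1 + 1 = 2 exceeded 2500 ng/mL.

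**The case against.** A fair defence has four parts.

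- **The condition is visible.** Section 8.2.5 prints n = 12 and p = 0.90 beside the 89%, introduces the rule conditionally, and disclaims formal power. This stands as mitigation. It does not justify a minimum, since nothing shows that 0.90 is a lower bound for p.
- **The focus on 500 ng/mL is explained.** Section 4.2.3 cites the link between low exposure and poor outcome, and sees no sign of toxicity tied to Cavg above 2500 ng/mL. That explains the choice in Section 8.2.5 but leaves Section 4.2.2 unreconciled. Section 4.2.2 also used the upper limit when it argued against 7.5 mg/kg.
- **Nothing is lost in reporting.** Section 8.2.1 summarises both proportions. This stands.
- **No action depends on the rule.** Cohort #3 is the final cohort and has no formal interim analysis. After Cohort #2 the sponsor judged the in-range target met and still added a cohort because mean Cavg was low. This also stands.

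A reader might infer more: that PFS in Age Group 1 clearly misses 89% under the above-500 wording. The documents do not support that. The 0.74 needs an added lognormal model, and scaling each Table 2 cell with its own GCV gives about 0.98. The predicted geometric mean of 847 ng/mL at 6 mg/kg is itself below the 976 ng/mL observed at 4.5 mg/kg. Those scalings rest on 5 and 7 subjects, so they do not establish that 89% is met either.

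Nor is Section 8.2.5 the only place with a success threshold; Section 4.2.2 states one too, which is the source of the inconsistency.

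**Conclusion.** The point holds as a minor one. The misprint and the two versions of the rule are plain on the page. The 89% is correct at p = 0.90 and is not shown to be a minimum: under the in-range version, the plan's own predictions give 0.80, 0.68 and 0.63 in three of four Cohort #3 cells. Under the above-500 version the answer for PFS in Age Group 1 is open, at about 0.66 to 1.00 depending on the assumptions.

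All these figures treat subjects as independent and assume 12 evaluable per cell. For PFS that number is not assured. Section 8.2.1 defines evaluability on IV therapy, and Section 5.9 replaces a subject who "fails to complete 7 days of IV study therapy, a replacement subject will be entered at that dose cohort and age group". The completed PFS cells in Table 1 had 5, 10, 7 and 8 subjects. The PFS probabilities are therefore indicative.

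It would be wrong to infer that the trial is too small or its analysis unsound. The trial is for estimation, and no sample size, analysis or Cohort #3 decision changes.

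**What to change.** Wording only, in Sections 8.2.5 and 4.2.2:

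1. Correct 82.2% to 83.3%.
2. Reconcile the two sections so that one version of the 10-of-12 rule is named as the criterion and the other as supportive. Which one is the sponsor's choice.
3. Delete *at least* before 89% and say that 89% is the value at an assumed p = 0.90 with 12 evaluable subjects. Alternatively, give the probability by formulation and age group.

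The cost is a few words. The alternative in item 3 needs P(Cavg > 500) from the existing simulation output if the above-500 version is chosen; the in-range figures already follow from Section 4.2.2. The only downside is that some stated probabilities may be less favourable.
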